11.6 Appendix 6. Sample Storage and Destruction

Any blood sample collected according to the Schedule of Activities () can be analyzed for any of the tests outlined in the protocol and for any tests necessary to minimize risks to study subjects. This includes testing to ensure analytical methods produce reliable and valid data throughout the course of the study. This can also include, but is not limited to, investigation of unexpected results, incurred sample reanalysis, and analyses for method transfer and comparability.

All samples and associated results will be coded prior to being shipped from the site for analysis or storage. Samples will be tracked using a unique identifier that is assigned to the samples for the study. Results are stored in a secure database to ensure confidentiality.

If informed consent is provided by the subject, Amgen can do additional testing on remaining samples (ie, residual and back-up) to investigate and better understand migraine, the dose response and/or prediction of response to erenumab, and characterize aspects of the molecule (eg, mechanism of action/target, metabolites). Results from this analysis are to be documented and maintained, but are not necessarily reported as part of this study. Samples can be retained for up to 20 years.

Since the evaluations are not expected to benefit the subject directly or to alter the treatment course, the results of pharmacogenetic, biomarker development, or other exploratory studies are not placed in the subject's medical record and are not to be made available to the subject, members of the family, the personal physician, or other third parties, except as specified in the informed consent.

The subject retains the right to request that the sample material be destroyed by contacting the investigator. Following the request from the subject, the investigator is to provide the sponsor with the required study and subject number so that any remaining blood samples and any other components from the cells can be located and destroyed. Samples will be destroyed once all protocol-defined procedures are completed. However, information collected from samples prior to the request for destruction, will be retained by Amgen.

The sponsor is the exclusive owner of any data, discoveries, or derivative materials from the sample materials and is responsible for the destruction of the sample(s) at the request of the subject through the investigator, at the end of the storage period, or as appropriate (eg, the scientific rationale for experimentation with a certain sample type no longer justifies keeping the sample). If a commercial product is developed from this research project, the sponsor owns

the commercial product. The subject has no commercial rights to such product and has no commercial rights to the data, information, discoveries, or derivative materials gained or produced from the sample. See Section [11.3](#) for subject confidentiality.

Amendment 2

Protocol Title: Biomarker and Genetic Predictors of Erenumab Treatment Response, a Phase 4 Investigational Open-label Study (INTERROGATE)

Amgen protocol Number Erenumab 20190006

NCT04265755

Amendment Date: 23 February 2022

Rationale:

This protocol is being amended to:

- Reduce the sample size from 2000 subjects to 1400 subjects throughout the protocol as the sites will not be able to achieve the enrollment target and it was determined that a lower sample will still provide sufficient analytical power.
- Update Sample Size Determination for align with the sample size.
- Update section on serious adverse events after the protocol-required reporting period, Product Complaints, Adverse Device Effect Definition, Serious Adverse Event Reporting via Electronic Data Collection Tool as per the latest template text.
- Increase the sample from 200 subjects to 315 subjects in optional CGRP biomarker substudy.
- Perform administrative and formatting updates.

Amendment 1

Protocol Title: Biomarker and Genetic Predictors of Erenumab Treatment Response, a Phase 4 Investigational Open-label Study (INTERROGATE)

Amgen Protocol Number Erenumab 20190006

Amendment Date: 01 February 2021

Superseding Amendment 15 March 2021

Date:

Rationale: Changes have been made to facilitate enrollment and provide subjects with flexibility, including the option to separate screening from the start of the baseline period; adding the option for self-administration of the investigational product on day 1, and a rescreening option. Changes were also made to clarify aspects of the protocol, including the collection of DNA samples from all subjects; requirements for allowable use of other migraine preventive medication; and calcitonin gene-related peptide assessments after day 1 to be only conducted in an optional sub-study. Updates were also made to reflect current data in the risk and statistical analysis sections.

The following changes have been made:

- The screening and baseline periods have been separated
- Statistical analyses have been updated
- Notes have been added to the schedule of assessments (SOA) to clarify activities
- Optional sub-study assessments have been put into a separate SOA
- References to some exploratory objectives have been removed
- Benefit risk-assessment language has been updated to reflect current assessments
- End of study language edited to reflect current template format
- Exclusion criteria 215 added: "Initiation, discontinuation, or change of dosing of migraine prophylactic medications within 2 months prior to the start of the baseline period, during the baseline period or planned during the study."
- Screen failure and rescreening language updated: a subject may be rescreened once if in the opinion of the investigator, the reason for the initial screen failure has been resolved or is no longer applicable
- Excluded treatments, medical devices, and/or procedures during the study period have been updated
- Hepatotoxicity sections have been removed per template language regarding it as optional
- Sampling has been updated for the plasma calcitonin gene-related peptide (CGRP) biomarker substudy
- Editorial and administrative updates have been made throughout

On 15 March 2021, the protocol amendment was superseded to include the following:

- To include CGRP samples for biomarker research
- Remove abbreviation drug induced liver injury (DILI) from the abbreviation list

Amendment 1

Protocol Title: Biomarker and Genetic Predictors of Erenumab Treatment Response, a Phase 4 Investigational Open-label Study (INTERROGATE)

Amgen Protocol Number Erenumab 20190006

Amendment Date: 01 February 2021

Rationale: Changes have been made to facilitate enrollment and provide subjects with flexibility, including the option to separate screening from the start of the baseline period; adding the option for self-administration of the investigational product on day 1, and a rescreening option. Changes were also made to clarify aspects of the protocol, including the collection of DNA samples from all subjects; requirements for allowable use of other migraine preventive medication; and calcitonin gene-related peptide assessments after day 1 to be only conducted in an optional sub-study. Updates were also made to reflect current data in the risk and statistical analysis sections.

The following changes have been made:

- The screening and baseline periods have been separated
- Statistical analyses have been updated
- Notes have been added to the schedule of assessments (SOA) to clarify activities
- Optional sub-study assessments have been put into a separate SOA
- References to some exploratory objectives have been removed
- Benefit risk-assessment language has been updated to reflect current assessments
- End of study language edited to reflect current template format
- Exclusion criteria 215 added: “Initiation, discontinuation, or change of dosing of migraine prophylactic medications within 2 months prior to the start of the baseline period, during the baseline period or planned during the study.”
- Screen failure and rescreening language updated: a subject may be rescreened once if in the opinion of the investigator, the reason for the initial screen failure has been resolved or is no longer applicable
- Excluded treatments, medical devices, and/or procedures during the study period have been updated
- Hepatotoxicity sections have been removed per template language regarding it as optional
- Sampling has been updated for the CGRP biomarker substudy
- Editorial and administrative updates have been made throughout

Table 7. Exploratory Efficacy Endpoint Summary Table to be Performed by deCODE	26
Table 8. Exploratory Efficacy Endpoint Summary Table to be Performed by Amgen	27

List of Abbreviations and Definition of Terms

Abbreviation or Term	Definition/Explanation
AE	Adverse event
AHMD	acute headache medication days
AMSMd	acute migraine-specific medication days
ANCOVA	Analysis of covariance
CGRP	calcitonin gene-related peptide
CM	chronic migraine
CTCAE	Common Terminology Criteria for Adverse Events
DARS	Data Acquisition Requirements Specification
DMP	Data Management Plan
DXDT	diagnosis date
EAS	efficacy analysis set
eCRF	electronic case report form
eDiary	electronic diary
EM	episodic migraine
EOS	End of study
FAS	full analysis set
GCP	Good Clinical Practice
GBS	Global Biostatistical Science
GSO-DM	Global Study Operations – Data Management
IP	Investigational Product
IPD	important protocol deviations
LSM	Least squares means
MAF	minor allele frequency
MedDRA	Medical Dictionary for Regulatory Activities
MFIQ	Migraine Functional Impact Questionnaire
MMD	monthly migraine day
mPRS	migraine polygenic risk score
NCT	National Clinical Trials
OLTP	Open-label Treatment Period
PRS	polygenic risk score
Q4W	Every 4 weeks
SAP	statistical analysis plan
SAE	serious adverse events
SAS	safety analysis set
SC	Subcutaneous
SNP	single-nucleotide polymorphism
TEAE	treatment-emergent adverse event

1. Introduction

The purpose of this Statistical Analysis Plan (SAP) is to provide details of the statistical analyses that have been outlined within the **Protocol Amendment 2** for Study 20190006, Erenumab dated **23 February 2022**. The scope of this plan, includes the portion of the final analysis which will be executed by the Amgen Global Biostatistical Science department. The remaining final analysis will be executed by deCODE as specified in the deCODE Analysis Plan ([Appendix B](#)).

2. Objectives, Endpoints and Hypotheses

2.1 Objectives and Endpoints

Objectives	Endpoints
Primary	

To explore the relationship between clinical response to erenumab and genetic biomarkers	
Achievement of at least a 50% reduction from baseline in mean monthly migraine days (MMD) over months 4, 5, and 6 in relation to each individual genome-wide significant single-nucleotide polymorphism (SNP) contributing to the migraine polygenic risk score (mPRS)

Objectives	Endpoints
Exploratory	

To describe the relationship between monthly AMSM use and mPRS in erenumab-treated subjects	
Change from baseline in monthly AMSMD over months 4, 5, and 6, in relation to mPRS

To describe the relationship between baseline calcitonin gene-related peptide (CGRP) levels and clinical response with erenumab treatment as assessed by MMD in erenumab-treated subjects	
Change from baseline in MMD over months 4, 5, and 6 in relation to baseline CGRP levelAchievement of at least a 50% reduction from baseline in mean MMD over months 4, 5, and 6 in relation to baseline CGRP levelAchievement of at least a 75% reduction from baseline in mean MMD over months 4, 5, and 6, in relation to baseline CGRP level

To describe the relationship between baseline CGRP levels and clinical response with erenumab treatment as assessed by monthly acute migraine-specific medication days (AMSMD) in erenumab-treated subjects	
Change from baseline in monthly AMSMD over months 4, 5, and 6, in relation to baseline CGRP level

Objectives	Endpoints
Exploratory (Continued)	

• To describe the relationship between mPRS and baseline CGRP	
• mPRS in relation to baseline CGRP level

• To describe the relationship between baseline CGRP levels and migraine disease characteristics	
• Baseline CGRP level in relation to baseline MMD• Baseline CGRP level in relation to baseline AMSMD• Baseline CGRP level in relation to baseline AHMD• Baseline CGRP level in relation to each MFIQ individual domain score (physical function, usual activities, social function, and emotional function) and overall impact usual activities global item score at baseline• Baseline CGRP in relation to presence of aura during baseline• Baseline CGRP in relation to baseline mean migraine severity

• To describe the relationship between mPRS and migraine disease characteristics	
• mPRS in relation to baseline MMD• mPRS in relation to baseline AMSMD• mPRS in relation to baseline acute headache medication days (AHMD)• mPRS in relation to Migraine Functional Impact Questionnaire (MFIQ) individual domain scores (physical function, usual activities, social function, and emotional function) and overall impact usual activities global item score at baseline• mPRS in relation to presence of aura during baseline• mPRS in relation to baseline mean migraine severity

Objectives	Endpoints
Exploratory (Continued)	

To evaluate the effect of erenumab as assessed by change in MMD in erenumab-treated subjects	
Change from baseline in mean MMD over months 4, 5, and 6Change from baseline in MMD at assessment timepointsAchievement of at least a 50% reduction from baseline in mean MMD over months 4, 5, and 6Achievement of at least a 50% reduction from baseline in MMD at assessment timepointsAchievement of at least a 75% reduction from baseline in mean MMD over months 4, 5, and 6Achievement of at least a 75% reduction from baseline in mean MMD at assessment timepoints

To evaluate the effect of erenumab as assessed by change in monthly AMSMD in erenumab-treated subjects	
Change from baseline in mean monthly AMSMD over months 4, 5, and 6Change from baseline in monthly AMSMD at assessment timepoints

To evaluate the effect of erenumab as assessed by change in monthly AHMD in erenumab-treated subjects	
Change from baseline in mean monthly AHMD over months 4, 5, and 6Change from baseline in monthly AHMD at assessment timepoints

To evaluate the effect of erenumab on functional impact as assessed by the change from baseline MFIQ score in erenumab-treated subjects	
Change from baseline in MFIQ individual domain scores (physical function, usual activities, social function, and emotional function) and overall impact usual activities global item score at month 6

To describe the relationship between change from baseline in MFIQ score and mPRS in erenumab-treated subjects	
Change from baseline in MFIQ individual domain scores (physical function, usual activities, social function and emotional function) and overall impact usual activities global item score at month 6, in relation to mPRS

2.2 Hypotheses and/or Estimations

No formal hypothesis testing will be performed. All analyses will be descriptive in nature.

3. Study Overview

3.1 Study Design

This is a phase 4 open-label study that will enroll subjects with episodic migraine (EM) or chronic migraine (CM) without a predetermined allocation ratio. The study will comprise the following periods:

- A screening period of up to 3 weeks (21 days) for the assessment eligibility criteria. The screening visit may be performed on the same day as the baseline visit
- A baseline period of 4 weeks (28 up to 35 days) to collect data on migraine headaches and acute headache medication use using electronic diary (eDiary) and to assess compliance in eDiary usage **at day 1 visit**
- A 24-week open-label treatment period

Subjects will be screened at the screening visit, and **if eligible, subjects may enter the baseline period at the same visit as screening or may begin baseline procedures up to 3 weeks after the screening visit.** At completion of the baseline period, those who **meet the eligibility criteria and** demonstrate $\geq 75\%$ compliance with eDiary use will be enrolled and will enter the open-label treatment period to receive erenumab either 70 mg or 140 mg subcutaneously (SC) every 4 weeks (Q4W) at the discretion of the investigator.

3.2 Sample Size

The primary objective is the identification of genome-wide significant SNPs contributing to the mPRS that are significantly associated with clinical response to erenumab treatment (based on achievement of at least a 50% reduction from baseline in mean MMD over months 4, 5, and 6). Based on erenumab pivotal EM and CM studies, the $\geq 50\%$ response rate with respect to MMD reduction is expected to be approximately 50% after 24 weeks of erenumab treatment. It is hypothesized that the mPRS SNPs with genome-wide significance ($p < 5 \times 10^{-8}$) have an additive effect on clinical response, ie, for each of these mPRS SNPs, each additional copy of the allele (with 0 as the reference) is associated with increased clinical response and will result in an odds ratio of 1.8 or higher (allelic odds ratio). **Given the currently known 123 migraine SNPs with genome-wide significance and a minor allele frequency (MAF) of at least 0.1, a study of 1400 subjects with 10% dropouts (resulting an effective sample size of 1260 at week 24) is at least 90% powered to identify five of the genome-wide significant migraine SNPs that are statistically significantly associated with clinical response. This is based on a two-sided power analysis, with Bonferroni adjustment, bootstrapping the data from the pivotal EM Study 20120296 ([Mikol et al, 2020](#)), using a logistic regression model to predict clinical response with each SNP, and adjusting for sex, age, BMI and principal components.**

4. Covariates and Subgroups

4.1 Planned Covariates

All models will be adjusted for age and sex. In addition, all model-adjusted analyses of efficacy endpoints assessing change from baseline will include the corresponding baseline value for the endpoint being analyzed. All models that compare baseline measurements only will be adjusted for country. However, country will not be included as a covariate in any deCODE performed analyses since all deCODE analyses will be performed separately by country (Denmark/Iceland) and subsequently combined in a meta-analysis. Due to the high correlation between baseline dose and country, models assessing change from baseline will instead be adjusted for baseline dose (70mg/140mg) and dose switch only.

Principal components of genotype data will be adjusted for population stratification in mPRS related analysis. Calculation of principal components data will be described in the analysis plan developed by deCODE.

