9.5 Efficacy Analyses

Detailed analysis methods and covariates included in the models are summarized in the table below.

Table 6. Analysis of Primary Efficacy Endpoint to be Performed by deCODE

Endpoint	Primary Summary and Analysis Method
Achievement of at least a 50% reduction from baseline in mean monthly migraine days (MMD) over months 4, 5, and 6 in relation to each individual genome-wide significant single-nucleotide polymorphism (SNP) contributing to	This analysis is planned to be performed by deCODE and details of the analysis are described in deCODE Analysis Plan (Appendix B).

Endpoint	Primary Summary and Analysis Method
the migraine polygenic risk score (mPRS)	

Table 7. Analysis of Exploratory Efficacy Endpoint to be Performed by deCODE

Endpoint	Primary Summary and Analysis Method
Change from baseline in monthly AMSMD over months 4, 5, and 6, in relation to mPRS	This analysis is planned to be performed by deCODE and details of the analysis are described in deCODE Analysis Plan (Appendix B).
mPRS in relation to baseline CGRP level	
mPRS in relation to baseline MMD	
mPRS in relation to baseline AMSMD	
mPRS in relation to baseline acute headache medication days (AHMD)	
mPRS in relation to Migraine Functional Impact Questionnaire (MFIQ) individual domain scores (physical function, usual activities, social function, and emotional function) and overall impact usual activities global item score at baseline	
mPRS in relation to presence of aura during baseline	
mPRS in relation to baseline mean migraine severity	
Change from baseline in MFIQ individual domain scores (physical function, usual activities, social function and emotional function) and overall impact usual activities global item score at month 6, in relation to mPRS	
Published migraine SNPs in relation to baseline CGRP	

Table 8. Analysis of Exploratory Efficacy Endpoints to be Performed by Amgen

Endpoint	Primary Summary and Analysis Method
Change from baseline in MMD over months 4, 5, and 6 in relation to baseline CGRP level	
 1. Summary statistics by visit using observed data at each visit, and the calculated mean monthly migraine days over month 4, 5 and 6. 2. Estimated slope for baseline CGRP, associated 95% CI and nominal p-value from a linear

Endpoint	Primary Summary and Analysis Method

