	
regression model including baseline CGRP, age, sex, dose switch (yes/no), baseline dose (full sample analysis only), and baseline MMD value as covariate using observed data. Dose switch was excluded for 140 mg treatment group.
 
3. Spearman correlation between baseline non-transformed CGRP and Change from baseline in MMD over months 4, 5, and 6.
 
4. A scatterplot with loess will developed for CGRP level with change from baseline in monthly MMD over months 4, 5, and 6.

Achievement of at least a 50% reduction from baseline in mean MMD over months 4, 5, and 6 in relation to baseline CGRP level	
1. Summary statistics based on observed data.2. Odds ratio estimate for baseline CGRP, associated 95% CI, and nominal p-value from a logistic regression model with baseline CGRP level as covariate along with baseline MMD, dose switch (yes/no), baseline dose (full sample analysis only), age and sex. Dose switch was excluded for 140 mg treatment group.3. Predicted probabilities of achieving at least a 50% reduction in MMD
Achievement of at least a 75% reduction from baseline in mean MMD over months 4, 5, and 6, in relation to baseline CGRP level	Same as above.
Change from baseline in monthly AMSMD over months 4, 5, and 6, in relation to baseline CGRP level	
1. Estimated slope for baseline CGRP, associated 95% CI and nominal p-value from a linear regression model including baseline CGRP, age, sex, dose switch (yes/no), baseline dose (full sample analysis only), and baseline AMSMD value as covariate using observed data. Dose switch was excluded for 140 mg treatment group.2. Spearman correlation analysis will be applied between baseline CGRP and change from baseline in monthly AMSMD over months 4, 5, and 6.3. A scatterplot with loess will developed for CGRP level with change from baseline in monthly AMSMD over months 4, 5, and 6.
Baseline MMD in relation to baseline CGRP level	
1. Summary statistics using observed data.2. Estimated slope for CGRP, associated 95% CI and nominal p-value from a linear regression model including age, sex, country (full sample analysis only), and baseline CGRP as covariate using observed data.3. Spearman correlation between baseline CGRP and baseline MMD.

Endpoint	Primary Summary and Analysis Method

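### Dropping country from the CGRP-response models because it correlates with dose does not protect the CGRP estimate and leaves some avoidable confounding by country

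*SAP*

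**What the plan says.** SAP 4.1 (Planned Covariates) has two rules for the sponsor's models. For cross-sectional baseline analyses, "All models that compare baseline measurements only will be adjusted for country". For change from baseline, "Due to the high correlation between baseline dose and country, models assessing change from baseline will instead be adjusted for baseline dose" and dose switch. The correlation is the only reason given. No value for it is stated, and no sensitivity model with country is planned.

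Table 8 in SAP 9.5 carries the second rule into every CGRP-response model:

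- Change in MMD: "regression model including baseline CGRP, age, sex, dose switch (yes/no), baseline dose (full sample analysis only), and baseline MMD value as covariate".
- 50% response, with 75% response handled the same way: "baseline CGRP level as covariate along with baseline MMD, dose switch (yes/no), baseline dose (full sample analysis only), age and sex".
- Change in AMSMD: the same terms, ending "baseline dose (full sample analysis only), and baseline AMSMD value as covariate using observed data".

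None contains country. By contrast, the model for baseline MMD against baseline CGRP is a "linear regression model including age, sex, country (full sample analysis only), and baseline CGRP as covariate using observed data". For change in MMD the reported result is "Estimated slope for baseline CGRP, associated 95% CI and nominal p-value from a linear" regression; the responder models report the CGRP odds ratio in the same way, plus predicted probabilities.

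Dose is not randomised. SAP 3.1 leaves it "at the discretion of the investigator". Analysis within country followed by meta-analysis applies, under SAP 4.1, only to the analyses that deCODE performs. The CGRP-response analyses are the sponsor's.

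**The concern.** In these models the target is the CGRP coefficient. Dose and country are both there only to adjust for other influences. If the two are highly correlated, their separate coefficients are hard to estimate, but nobody reports those coefficients here. Removing one does not sharpen the CGRP estimate. It does remove protection if CGRP and response both differ between Iceland and Denmark in ways that dose, age, sex and the baseline value do not capture.

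The SAP already treats country as worth adjusting for when CGRP is related to baseline migraine measures. It then leaves it out when CGRP is related to response, which is the more interesting question. At stake is whether a CGRP-response slope can be read as something other than a difference between two countries.

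The terms marked for the full sample only, and the note that dose switch is excluded in the 140 mg group, imply further runs within dose group. There baseline dose is constant, so its correlation with country cannot be a reason to omit country, yet those models have no country term either.

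**Working it through.** There is no figure in the plan to reproduce for this choice. The only document number used is the analysable sample in SAP 3.2: 1400 × (1 - 0.10) = 1260.

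**Assumptions (not in the documents).** Country and dose each split 50/50 with correlation r. CGRP has within-country SD 1 and differs by d between countries. Response differs by G days between countries, with residual SD 4 days. There is no true CGRP effect, and within country CGRP does not influence the dose chosen. Ranges: d = 0.3, 0.5, 1.0; G = 1, 2; r = 0.6 to 0.95.

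**Formulas.** The variance of country left over after adjusting for dose is k = ¼(1 - r²).

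- Bias of the CGRP slope, dose only: b = Gdk / (1 + d²k).
- Its standard error: SE² = [16 + G²k/(1 + d²k)] / [1260(1 + d²k)].
- With country added: bias 0, SE = 4/√1260 = 0.113.
- Rejection rate of the two-sided 5% test: Φ(b/SE - 1.96) + Φ(-b/SE - 1.96).

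With no adjustment, k is ¼. Adjusting for dose therefore leaves about 1 - r² of the bias.

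**One case in full.** r = 0.8, d = 0.5, G = 2. Then k = 0.25 × 0.36 = 0.09 and 1 + d²k = 1.0225. The bias is 2 × 0.5 × 0.09 / 1.0225 = 0.088 days per SD of CGRP. SE² = (16 + 0.352)/(1260 × 1.0225) = 0.0127, so SE = 0.113. b/SE = 0.78, and the rejection rate is Φ(-1.18) + Φ(-2.74) = 12.2%.

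**Range, dose only:**

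| r | 1 - r² | Rejection, all but the largest pair of gaps | Rejection at d = 1.0, G = 2 | Bias there (days per SD) |
|---|---|---|---|---|
| 0.60 | 64% | 7.1% to 27.7% | 73.6% | 0.276 |
| 0.80 | 36% | 5.7% to 12.2% | 32.8% | 0.165 |
| 0.90 | 19% | 5.2% to 7.0% | 13.0% | 0.091 |
| 0.95 | 10% | 5.0% to 5.5% | 7.1% | 0.048 |

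Simulation of the same linear model agrees within Monte Carlo error: about 4% to 8% at r of 0.9 or more (13% at r = 0.9 with both gaps largest), about 7% to 12% at r = 0.8 (35% at the corner), and about 73% at the r = 0.6 corner. With country in the model it stays at about 4% to 6.5%.

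**Price of adding country.** The CGRP standard error goes from 0.105-0.114 to 0.113. The largest increase is at r = 0.6, d = 1.0: √(1 + 0.16) = 1.08, so about 8% at most; at r = 0.9 it is about 2%. What collinearity does inflate is the variance of the dose coefficient, by 1/(1 - r²): 2.8 at r = 0.8, 5.3 at 0.9, 10.3 at 0.95.

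**Logistic form.** A small simulation (400 runs per setting, 50% response, country log-odds difference 0.5, r = 0.8 and 0.9) gave a standard error for the CGRP log odds ratio 0.4% to 1.5% larger with country for d up to 0.5, and at most 4.6% larger (d = 1.0, r = 0.8).

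**The case against.** The best defence is that dose stands in for country. The stronger the correlation the SAP asserts, the less confounding remains, and with 2 to 4 sites (protocol 4.2.2) and dose chosen by the investigator, a very high correlation is plausible. This stands as a limit on size: at r = 0.9 or above the residual effect is small unless both country gaps are large. It does not rescue the rationale, because high correlation makes the omission less harmful, never useful, for the CGRP coefficient.

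A second defence is that one covariate set for all change models is tidy, and that the least-squares-mean models in Table 8 do have a dose term that country would destabilise. That is fair for those models. They estimate no CGRP effect, so the point does not cover them.

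A third is that adding a covariate to a logistic model alters what its odds ratio conditions on. True, but the baseline-only aura model already conditions on country.

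A reader might go further than the documents allow:

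- That the CGRP-response models alone pool the countries without a country term. The MFIQ ANCOVA and the mixed models for MMD, AMSMD and AHMD do so too.
- That a false CGRP finding is likely. Rejection rates near 73% need the lowest correlation tried together with the largest gaps, which sits badly with a correlation called high. Nothing in the documents shows that CGRP or response differs by country.
- That p-values will be too small. The bias can create an association or mask one.

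**Conclusion.** The stated reason for replacing country with dose does not apply to the models that report a CGRP slope or odds ratio. Country can be added at almost no cost in precision, and leaving it out keeps roughly 1 - r² of any country confounding.

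How much that matters cannot be settled from the documents; it rests on the assumed correlation, country gaps and 50/50 splits. On those assumptions it is minor at r of 0.9 or more and noticeable at 0.8 or below when the gaps are moderate to large. The analyses are exploratory, with nominal p-values, in a study described as having no formal hypothesis tests. The primary SNP analysis is run within country and is untouched. This is a modest-priority correction, not a threat to the trial's main result.

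**What to change.** In SAP 4.1 and Table 8:

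- Add country beside baseline dose in the full-sample linear and logistic CGRP-response models, or fit them within country and combine.
- Add country to the by-dose runs wherever both countries are represented in the dose group.
- Withdraw the collinearity rationale for these models, and leave the separate dose and country coefficients uninterpreted.
- Keep the dose-only model as a sensitivity analysis.
- Report the baseline dose-by-country table, so that readers can see how well dose stands in for country.

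The cost is one model term, some SAP wording and one small table. No new data are needed.
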